Aim 3 will determine immediate and prolonged psychological reactions to biomarker disclosure among participants with MCI and DAT and their respective co-participants (e.g., care partners). We will assess changes in psychological status (both positive and negative) at two time points following disclosure relative to baseline. While one could predict changes in either direction, the above noted paucity of data in this area undermine the validity of such predictions. Thus, this aim is more descriptive in nature and provides critical information about cognitively symptomatic participants’ response to biomarker disclosure that will guide future research and translational efforts.

Aim 4 examines the impact of biomarker disclosure on co-participants as it relates to caregiving readiness and self-efficacy. We will assess changes in perceived readiness to provide care (to the participant) and caregiving self-efficacy at two time points following disclosure relative to baseline among co-participants who are either currently providing care to participants with MCI/DAT or who will hypothetically take on the caregiving role should the need arise. We predict that caregiving preparedness will be associated with the participant’s disclosed amyloid/tau result; specifically, an ‘elevated’ biomarker result is hypothesized to be associated with greater caregiving preparedness. Conversely, it is hypothesized that co-participants will have lower perceived readiness for caregiving if the participant’s amyloid/tau result is ‘not elevated.’

SECTION 2.3: Trial Design

The Education portion of the study is considered a Phase I/II Behavioral Intervention clinical trial without randomization. The Disclosure portion of the study is considered a Phase I/II Behavioral Intervention clinical trial without randomization, with the disclosure feedback serving as the intervention. The study will use a single-group design. All 100 participants (and any co-participants attending the first session) will complete the educational presentation and undergo an assessment of comprehension and decisional capacity. Those participants or dyads who meet criteria and demonstrate intact decisional capacity will be offered feedback about the participant’s PET amyloid and tau results. Outcomes will be measured immediately following feedback, within one week of disclosure, and at six-weeks post-disclosure. For more information regarding design, see *Methods* section.

SECTION 3: METHODS

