If the participant does not demonstrate disclosure decision-making capacity and does not have a co-participant or LAR/DPOA, the participant's involvement in the study will be complete after this session, and they will not be invited to take part in the Part II Disclosure portion.

If the participant has a LAR/DPOA co-participant, that individual must demonstrate decision-making capacity for the participant to receive risk disclosure and agree with this decision. Participant decision-making capacity will still be assessed. Regardless of whether the LAR/DPOA wants the participant to complete risk disclosure, the study team will not move forward with sharing the participant's risk information with either party unless assent is provided by the participant. If the participant or designated LAR/DPOA does not demonstrate full decision-making capacity, the study team will not move forward with risk disclosure, and the dyad's involvement in the study will be complete.

If the participant brings a co-participant who is not the designated LAR/DPOA, the participant may allow that individual to make the decision regarding PET disclosure for them. If this option is selected, the co-participant will undergo disclosure decision-making capacity assessment. Participant decision-making capacity will still be assessed. Regardless of whether the co-participant wants the participant to complete risk disclosure, the study team will not move forward with sharing the participant's risk information with either party unless assent is provided by the participant. If the participant or designated co-participant does not demonstrate full decision-making capacity, the study team will not move forward with risk disclosure, and the dyad's involvement in the study will be complete.

4. Baseline Outcome Measurement (for Part II): In order to gather baseline measurements of the constructs of interest for Part II of the study, all participants in Part I will complete the five outcome measures listed in Section 3.4.

Table 2. Proposed Components of Part I Education

1. Consent for Education (may be completed pre-session; separate)

2. Education Presentation (participant with co-participant)
3. Participant Decision-Making Capacity Assessment (separate)
4. Co-Participant or LAR/DPOA Decision-Making Capacity Assessment (separate)
5. Participant & Co-Participant Baseline Outcome Measurement (separate)
6. Post-Session study team review of responses to determine Disclosure eligibility

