3.4 OUTCOMES

In addition to measuring **preliminary interest in PET disclosure after STIM activities (Aim 1, Primary Outcome 1)** and **Disclosure Decision-Making Capacity (overall and by component; Aim 2, Primary Outcome 2)**, we will collect the following outcome measures post-disclosure for participants who complete this step (Aim 3). These measures will be completed over the phone or via virtual visit to allow for maximum flexibility. Of note, we will also administer the GDS-15 and BAI at each time point for the purpose of safety monitoring (see DSMP); these are not considered primary outcomes. A summary of the outcome measure respondents and timeline is provided in Table 4.

Primary Outcome 3.1 - Comprehension & Recall: The Personal Information and Meaning of Information accuracy scores will be totaled for all participants and co-participants. Mean, median, and standard deviation will be calculated. Exploratory analyses will evaluate trends in whether specific types of feedback information (e.g., neuroimaging vs. amyloid/tau burden) were better understood than others, and whether group differences exist (i.e., participants vs. co-participants, by race, by cognitive status).

Primary Outcome 3.2 - Positive and Negative Affective Scale – Short Form (PANAS-SF¹⁸): This 20-item scale asks respondents to rate the extent to which they are experiencing positive (e.g., excited, inspired) and negative (e.g., distressed, ashamed) emotions on a Likert-style scale ranging from '1 = Very Slightly or Not at All' to '5=Extremely.' The two subscale scores range from 10-50, with higher scores indicating higher positive or negative emotions, respectively. The PANAS has demonstrated strong psychometric properties for assessing emotions in older adults¹⁹. This measure will be administered to both participants and co-participants.

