Primary Outcome 3.3 - Impact of Neuroimaging in Alzheimer's Disease (INI-AD): This measure assesses both positive and distressing reactions to disclosure of PET amyloid and tau results. The measure is adapted from the original Impact of Genetic Testing in Alzheimer's Disease scale²⁰ (used to measure reactions to genetic susceptibility testing results for AD genes), the scale was adapted to PET biomarker disclosure. This scale has been previously developed and used as part of the REVEAL study, and has the strength of assessing both positive and negative reactions and being specific to Alzheimer's disease. This measure will be administered to both participants and co-participants.

Primary Outcome 3.4 - Stigma Scale for Chronic Illness (SSCI-8²¹): The SSCI-8 demonstrates strong reliability for the measurement of both internalized and enacted stigma perceived by individuals with chronic neurological conditions. Respondents complete 8 items about experiences of stigma, rated on a Likert-style scale from 1 = 'Never' to 5 = 'Always.' This measure will be administered to participants only.

Primary Outcome 3.5 - Self-Efficacy for Managing Chronic Disease Scale (SECD²²): The SECD is a 6-item scale that measures perceived ability to self-manage the physical, emotional, and cognitive symptoms associated with their chronic disease. Items are listed on a 10-point scale ranging from 1 = 'Not at all confident' to 10 = 'Totally confident'. Though not previously applied to Alzheimer's disease specifically, psychometric properties for the assessment of self-efficacy across chronic conditions were strong (reliability ranging from 0.88-0.95²³). This measure will be administered to participants only.

Primary Outcome 3.6 - Future Time Perspective Scale (FTP²⁴): This 10-item scale measures the extent to which respondents feel that they have potential for productive and functional years ahead of them. Statements regarding positive and negative future time perspective are rated on a 7-point Likert-style scale, ranging from 1= 'Very untrue' to 7='Very true.' This measure will be administered to both participants and study partners.

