3.5.2 Statistical Design

Data Screening

Prior to statistical analyses, data screening will be conducted. Initial steps will include a missing data analysis to determine randomness of missing data and range checks to assess for data quality. Additional screening for univariate and multivariate outliers, skewness and kurtosis will be conducted to inform needs for data transformation and statistical approach.

Statistical Approach

To assess Aim 1, we will compare the proportion of individuals in each diagnostic group who request vs. completed disclosure using a chi-squared test. Similarly, we will test hypotheses associated with Aim 2 (*greater disclosure decisional capacity in MCI than DAT*) by comparing the proportion of individuals in the DAT and MCI groups who demonstrate 'pass' scores on the DDMAT using a chi-squared test. We will also explore which particular elements of decision-making capacity may be more impaired in each group by comparing proportion of each diagnostic group who can adequately demonstrate understanding, appreciation, rationale, and communication on the DMAT using the same statistical strategy. To evaluate Aim 3, (*psychological reactions based on biomarker status*) we will compare participants' and co-participants' responses on outcome measures, based on amyloid and/or tau positivity vs. biomarker negativity. As we expect outcome measures to be correlated, we will utilize a 2 (diagnosis: MCI vs. DAT) by 2 (biomarker status: positive vs. negative) repeated measures analysis of variance (rmANOVA) approach for each follow-up time point. We will also compare differences in psychological reactions between participants and co-participants by diagnosis (MCI vs. DAT) using a paired t-test on all continuous items and a chi-squared test on categorical items. To evaluate Aim 4 (*impact of biomarker disclosure on co-participant caregiving readiness and self-efficacy*), we will similarly compare co-participants' responses, based on amyloid and/or tau positivity vs. biomarker negativity. As we expect outcome measures to be correlated, we will utilize a 2 (participant's diagnosis: MCI vs. DAT) by 2 (biomarker status: positive vs. negative) repeated measures analysis of variance (rmANOVA) approach for each follow-up time point.

SECTION 4: MONITORING

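### The Aim 3 and Aim 4 repeated-measures ANOVA names neither its within-subject factor nor its test of interest; read literally, it tests biomarker status on a raw average of unlike scales

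*Combined protocol and SAP*

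**What the plan says.** Section 3.5.2 (Statistical Approach) gives the Aim 3 model and its reason: "As we expect outcome measures to be correlated, we will utilize a 2 (diagnosis: MCI vs. DAT) by 2 (biomarker status", the second factor being positive against negative. The model is a "repeated measures analysis of variance (rmANOVA) approach for each follow-up time point". Aim 4 uses the same wording with the participant's diagnosis. Both listed factors are between-subject. The section does not say what is repeated, whether there is one model per scale, or which term answers the question.

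Elsewhere, outcome measures means the questionnaires: section 3.3.1 item 4 says "all participants in Part I will complete the five outcome measures listed in Section 3.4", and Table 4, which summarises the outcome measures, lists scales.

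The scales differ in range and direction (section 3.4). For PANAS, "The two subscale scores range from 10-50, with higher scores indicating higher positive or negative emotions, respectively". SSCI-8 has 8 items scored 1 to 5, with higher meaning more stigma. For the 6-item SECD, "Items are listed on a 10-point scale ranging from 1" to 10, with higher meaning more confident. FTP has 10 items scored 1 to 7. Whether SECD and FTP are summed or averaged is not stated. Section 3.5.2 mentions transformation only after outlier, skewness and kurtosis screening; it plans no standardisation or reverse-scoring.

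Section 2.2 states the objectives as change. Aim 3: "We will assess changes in psychological status (both positive and negative) at two time points following disclosure relative to baseline". Aim 4 covers readiness and "caregiving self-efficacy at two time points following disclosure relative to baseline".

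**The concern.** A repeated-measures ANOVA needs repeats of one quantity. Correlation between different questionnaires does not supply that. If the scales are the repeats at a visit, the biomarker main effect compares groups on each person's unweighted mean across scales. A rise in negative affect then offsets a fall in positive affect, and a scale with a wide raw range outweighs a narrow one.

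These scales are designated primary outcomes, and this is the only biomarker comparison named for them. The stated purpose (section 2.1 background) is to look at positive and negative reactions alike, which an average across them obscures. A result that depends on whether one questionnaire is summed or averaged is also hard to interpret.

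**Working it through.** The plan gives no power, alpha or effect size for these aims, so there is no figure to reproduce.

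**Inputs from section 3.4.** Ranges as totals: PANAS positive 10-50, PANAS negative 10-50, SSCI-8 8-40 (8 x 1 to 8 x 5), SECD 6-60 (or 1-10 as an item mean), FTP 10-70.

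**Assumed inputs.** SD = range/6; correlation 0.3 after aligning directions; two-sided 5%; 35 v 35 by biomarker status; shifts of 0.7 SD; FTP keyed so that higher is better. Diagnosis is left out for simplicity, and INI-AD because its range is not given.

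**Reading 1: scales as repeats at one visit.** SDs are 6.67, 6.67, 5.33, 9.00 (SECD sum) or 1.50 (SECD item mean), and 10.00. The main effect has standardised size d = (sum of raw shifts) / sqrt(V), where V is the variance of the sum of the five scores. With signs +, -, -, +, + for direction:

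- SECD summed: the squared SDs add to 298.3; the signed SDs add to 13.67; V = 298.3 + 0.3 x (13.67² - 298.3) = 264.9, and sqrt(V) = 16.27.
- SECD item mean: 219.6; 6.17; V = 219.6 + 0.3 x (6.17² - 219.6) = 165.1, and sqrt(V) = 12.85. SECD then carries 2.25/219.6 = 1% of the summed variance and FTP 100/219.6 = 46%.

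The noncentrality is d x sqrt(35/2) = 4.18d on 68 df. One scale tested alone (d = 0.7) has 82% power. Examples of d:

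- PANAS positive down and negative up: -4.67 + 4.67 = 0, so d = 0.
- SECD alone: 1.05/12.85 = 0.08 (item mean) or 6.30/16.27 = 0.39 (sum).
- All five worse: 4.32/12.85 = 0.34 (SECD item mean) or 9.57/16.27 = 0.59 (sum).

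Interaction rates come from simulation with the Greenhouse-Geisser correction.

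| Shift of 0.7 SD | SECD scoring | Status main effect | Status x scale | One scale alone |
|---|---|---|---|---|
| PANAS positive down, negative up | item mean | 5% | 81% | 82% |
| PANAS positive down, negative up | sum | 5% | about 75% | 82% |
| SECD down only | item mean | 6% | 6% | 82% |
| SECD down only | sum | 36% | 58% | 82% |
| All five worse | item mean | 28% | 98% | 82% |
| All five worse | sum | 68% | 98% | 82% |

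With 0.5 SD harm on all five scales and 50 v 50, the main effect is -0.42 SD if all are totals, -0.24 SD if SECD alone is an item mean, and +0.15 SD if SECD and FTP are item means. The sign reverses on scoring alone.

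**Aim 4 on reading 1.** PCS (0-32 total, 0-4 mean) and the caregiving self-efficacy subscale both run towards better, so direction does not cancel. With 0.5 SD on both, 50 v 50 and correlation 0.3, d is 0.51 to 0.62. With 0.5 SD on PCS alone, d runs from 0.02 (chance-level rejection) to 0.45 (about 60% power). This depends on PCS scoring and on the self-efficacy range, which is not stated and was assumed as 1-10 mean, 5-50 total or 0-100 mean.

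**Reading 2: baseline against one follow-up, one scale at a time.** With baseline correlation r, the biomarker main effect tests the mean of the two occasions: d = 0.35 / sqrt((1 + r)/2). This is 0.40 at r = 0.5 and 0.38 at r = 0.7, giving 38% and 35% power at 35 v 35. Status x time has d = 0.7 / sqrt(2(1 - r)), which is 0.70 and 0.90, giving 82% and 96%. Table 4 schedules no pre-disclosure INI-AD, so this model cannot be run for it.

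**The case against.** The strongest defence is that reading 1 is not settled. Section 2.2 frames both aims as change from baseline, section 3.3.1 item 4 collects the measures in Part I as a baseline, and Table 4 schedules a baseline for every listed scale except INI-AD. A two-occasion ANOVA per scale, run for each follow-up, is ordinary practice, and nothing is then added across scales. This stands as a permissible reading. It does not rescue the text: correlated outcome measures would no longer be the reason for the model, INI-AD is left without an analysis, and the status x time term, on which this reading depends, is not named.

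A reader might infer from the cancellation that the whole model would miss opposite reactions. The figures do not support that. Status x scale picks up the PANAS pattern about as often as a single-scale test, and section 3.5.2 does not make the main effect the only test. The interaction does not say which scale moved, however, and it depends on units. The near-complete miss occurs for SECD alone under mixed scoring, which is an assumption because the scoring is not stated.

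A reader might also extend cancellation by direction to Aim 4, or infer that a null result would be reported as good tolerability. The Aim 4 scales run the same way. No passage says how a null would be read, section 2.2 calls Aim 3 mainly descriptive, and individual distress is monitored separately with GDS-15, BAI and INI-AD cut-offs (sections 4.1.1 and 4.1.2).

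**Conclusion.** The concern holds as an under-specified model whose most literal reading is unsuitable. The within-subject factor and the test of interest must be named for both aims. On the literal reading, the Aim 3 main effect can cancel completely (5% against 82%) and can change sign with scoring; in Aim 4 only the dependence on units applies. The interaction recovers much of the loss (about 75-81% and 98% in two scenarios), but it falls to 6% for SECD alone with mixed scoring. On the alternative reading, the main effect is diluted to 35-38% power against 82-96% for status x time, and INI-AD is not covered.

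The percentages rest on assumed SDs, correlations, effect sizes and group split. The exact PANAS cancellation needs only equal and opposite raw shifts on the two subscales. The documents do not establish that the sponsor intends to sum scales.

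**What to change.** In section 3.5.2, for Aims 3 and 4:

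- Replace the cross-measure ANOVA with one longitudinal model per scale or subscale: PANAS positive, PANAS negative, SSCI-8, SECD, FTP, PCS and caregiving self-efficacy. Use baseline and the follow-ups scheduled in Table 4.
- Name biomarker status x time as the test of interest, or the baseline-adjusted status effect at each follow-up, with diagnosis as a factor.
- Analyse the INI-AD positive and distress subscales on post-disclosure visits only.
- State how each scale is scored (sum or item mean, and reverse-keying) and how multiplicity is handled.
- If one cross-scale test is wanted, use MANOVA or a pre-stated composite of standardised, direction-aligned scores.

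The change is to wording only and needs no new data. The cost is more separate tests (nine scores in the list above), so error control has to be stated.

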3.5.1 Data Management & Entry

Only IRB approved study personnel will have access to study documents/data. Signed consent paperwork and will be uploaded into the participant's medical record according to IRB standards. Electronic consent forms will be saved under password protection on the secure lab drive. Copies will be printed and stored in the aforementioned binder, away from all other study data. Data are kept in a locked file cabinet within a locked, private office in an office suite (i.e., behind two locked doors). The participant's study ID number will be recorded on every paper page of the study documents. A centralized database for all outcomes will be saved on the University of Michigan secure server as a password-protected file only accessible by approved study personnel.

The participants' PET amyloid and tau data will not be requested or added to this database until completion of Part I Education & Decision-Making Assessment, to ensure no implicit bias in the manner in which Part I procedures are conducted based on participant risk. At this time, data from eligible participants enrolled in the Part II Disclosure will be accessed. De-identified participant information, coded with the parent study ID number, will be shared with the study team as a secure excel database and transferred to the centralized study database.

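### Aims 3 and 4 ask about change from baseline, but for the six scales with a pre-disclosure value section 3.5.2 does not say that baseline enters the analysis or which term is the test

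*Combined protocol and SAP*

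**What the plan says.** **Aims (section 2.2).** Aim 3: "We will assess changes in psychological status (both positive and negative) at two time points following disclosure relative to baseline". Aim 4 likewise covers changes in readiness to provide care and "caregiving self-efficacy at two time points following disclosure relative to baseline". Aim 3 is described as mainly descriptive. Aim 4 carries a directional prediction, that an elevated "biomarker result is hypothesized to be associated with greater caregiving preparedness".

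**Data (section 3.3.1, item 4, and Table 4).** Outcome measures are completed at the Education session, with the stated purpose: "In order to gather baseline measurements of the constructs of interest for Part II of the study". Table 4 marks a pre-disclosure value for PANAS-SF, FTP, SSCI-8, SECD, the caregiving self-efficacy scale and the Preparedness for Caregiving Scale. The INI-AD has none, and comprehension/recall is not listed there.

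**Analysis (section 3.5.2).** For Aim 3, responses are compared by amyloid and/or tau positivity using a "2 (diagnosis: MCI vs. DAT) by 2 (biomarker status: positive vs. negative) repeated measures analysis of variance (rmANOVA) approach for each follow-up time point". The reason given is "As we expect outcome measures to be correlated". Aim 4, labelled "impact of biomarker disclosure on co-participant caregiving readiness and self-efficacy", gets the same model in co-participants.

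**Timing of results (section 3.5.1).** The participants' "PET amyloid and tau data will not be requested or added to this database until completion of Part I Education & Decision-Making Assessment".

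**The concern.** The aims ask how people change after disclosure. The analysis section asks how responses differ between biomarker groups at each follow-up and does not say where baseline enters. Because status is observed and not assigned, the groups may already differ on these scales. Results are withheld during Part I, so a baseline gap could not come from results learned in this study. It would have to come from symptoms, parent-study experience or selection. The diagnosis factor removes only the part of it that MCI versus DAT explains.

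Aim 4 is the more exposed because it is directional: a gap present before disclosure could appear to support the prediction, or an opposite gap could hide a real difference in change. For Aim 3 error rates matter less, but an analysis without baseline would describe levels and not the promised change.

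**Working it through.** **Step 1: three readings of the model.** Let g be the gap between biomarker-positive and biomarker-negative groups at baseline, and δ the difference between them in change from baseline.

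- (a) Follow-up scores of one scale only. The status contrast is g + δ.
- (b) Several correlated scales as the repeated factor at one follow-up, which the stated reason for the model suggests. The status contrast is the average of g + δ over those scales. Baseline is still absent.
- (c) Baseline versus that follow-up as the repeated factor. The status main effect is [g + (g + δ)]/2 = g + δ/2, so it carries the whole gap and half of the difference in change. The status-by-time term is (g + δ) − g = δ.

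Only the last term answers the aims as stated, and section 3.5.2 does not name it under any reading. No other section does. The language about change in sections 4.1.1 and 4.3 concerns GDS-15 and BAI safety monitoring.

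**Step 2: inputs for an illustration.** There is no figure in the plan to reproduce. It gives no alpha, power, SD, baseline/follow-up correlation, biomarker split, DAT share or analysed number; 100 is an upper estimate of those invited to enrol. Everything below is therefore assumed: two-sided alpha 0.05, SD 1, about 40% DAT in each biomarker group, 55 positive/25 negative or 34/16 analysed, correlation r of 0.5 or 0.7, and a gap that is stable and not explained by diagnosis. One scale is analysed, so the figures describe readings (a) and (c) and not (b).

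**Step 3: standard errors.** For the status effect in a 2 × 2 model with interaction, SE = ½ × √(Σ 1/n_cell).

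- 55/25, cells 33, 22, 15, 10: ½ × √(0.0303 + 0.0455 + 0.0667 + 0.1000) = 0.246
- 34/16, cells 20, 14, 10, 6: ½ × √(0.0500 + 0.0714 + 0.1000 + 0.1667) = 0.312

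For change, multiply by √(2(1 − r)): 1.000 at r 0.5 and 0.775 at r 0.7. For the mean of baseline and follow-up, multiply by √((1 + r)/2): 0.866 and 0.922. Rejection probability comes from a noncentral t with N − 4 degrees of freedom and noncentrality contrast/SE.

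**Step 4: results.** Where two values are given, they are for r 0.5 / r 0.7.

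| Scenario | Test | 55/25 | 34/16 |
|---|---|---|---|
| g = 0.3, δ = 0 | Follow-up only | 23% | 16% |
| g = 0.3, δ = 0 | Status main effect under (c) | 28% / 26% | 19% / 18% |
| g = 0.3, δ = 0 | Status by time | 5% | 5% |
| g = −0.3, δ = 0.5 | Follow-up only | 13% | 10% |
| g = −0.3, δ = 0.5 | Status by time | 52% / 73% | 35% / 53% |
| g falls from 0.5 to 0.25 without any response | Follow-up only | 17% | 12% |
| g falls from 0.5 to 0.25 without any response | Status by time | 17% / 25% | 12% / 17% |

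For example, in the first row at 55/25, 0.3/0.246 = 1.22 against a critical value of 1.99 gives 23%. Simulation under the same assumptions (40,000 replicates per setting) agrees to within about one percentage point.

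**Step 5: sensitivity.** With a gap of 0.1 SD, follow-up only rejects in about 7% (55/25) or 6% (34/16), so a small gap matters little. At 0.5 SD the figures are 52% and 35%. A gap that arises wholly through diagnosis leaves follow-up only at 5%, because diagnosis is in the model.

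**The case against.** **A reader might infer that the plan is, as written, a follow-up-only comparison that discards baseline.** The text does not support that. One scale at one follow-up has no repeated measure, so a repeated measures model is not literally follow-up only. Given the aims and the stated purpose of the baseline data, baseline versus each follow-up is a natural reading. Under it, the right term is already in the model and the defect is that it is not named. This stands, and it limits the point to an omission in specification. It does not remove the point: the reason given for the model suggests correlated scales as the repeated factor, and that reading leaves baseline out.

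**The Aim 4 hypothesis is worded as an association.** A comparison at follow-up would test that sentence. This also stands. But the sentence that opens the aim speaks of changes relative to baseline, and section 3.5.2 speaks of impact, so the protocol's own wording is mixed and needs settling.

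**No gap is documented.** Correct. The exclusion at GDS-15 of 9 or more or BAI of 16 or more, for participants and co-participants (section 3.3.1), may also narrow baseline differences in affect. The percentages show sensitivity to a gap and are not expected error rates.

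**Status by time is not always better.** Also correct. If a 0.5 SD gap halves on its own, it does no better than follow-up only at r 0.5 and worse at r 0.7. Its advantage depends on the gap being stable, which the documents neither support nor refute.

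**Conclusion.** The omission is clear. For six scales the aims are stated as change from baseline, while section 3.5.2 neither identifies the repeated factor nor names a baseline level, change score or status-by-time test. Confidence in that is high.

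Confidence in the consequence is moderate, because it depends on which reading is meant and on a gap of unknown size. Under the assumptions above, a stable 0.3 SD gap takes a nominal 5% to about 23% (55/25) or 16% (34/16) for a follow-up-only comparison. An opposite gap cuts power for a true 0.5 SD difference in change at 55/25 to 13%, against 52% to 73% for status by time.

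Two stronger conclusions might be drawn and are not supported. The documents do not show that the biomarker groups differ at baseline. Nor would the corrected analysis isolate the effect of disclosure: the design has a single group with no undisclosed comparison, so it shows only whether the result groups change differently. This is a cheap improvement and does not invalidate the design.

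**What to change.** In section 3.5.2, for the six scales with a pre-disclosure value:

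- Make baseline versus each scheduled follow-up the within-person factor, or equivalently analyse change from baseline, with diagnosis and biomarker status between persons.
- For Aim 4, name status by time at each follow-up as the test, and align the hypothesis sentence in section 2.2 with it.
- For Aim 3, report overall change from baseline (the time effect) and the difference in change by status (status by time) as estimates with confidence intervals.
- Report baseline means by biomarker status.
- Analyse the INI-AD and comprehension/recall as post-disclosure-only outcomes.
- State that the comparison assumes any gap would otherwise stay stable, and that it shows differential change between result groups and not the effect of disclosure itself.

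Baseline as a covariate is not an interchangeable substitute here, because status is not randomised. In a simulation with 100 people split equally, r 0.6 and no difference in change (all assumed), it rejected in 11% of trials at a lasting gap of 0.3 SD and in 24% at 0.5 SD.

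The cost is wording and slightly more analysis, with no new data, visits or participants. The statistical price is power when there is no gap and r is below 0.5. At r 0.3 and 55/25, the SE for change is 0.246 × √1.4 = 0.291, and power for a 0.5 SD difference is 40% against 52% for follow-up only. At r 0.5 the two are equal.
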